### **Adherence and protocol deviations**

Attrition rates will be reported for both groups (received individually delivered vs. group-based CBTgrief). We will make the following categories: 1) Non-starters (participants that were randomized but received no therapy sessions), 2) Completers (participants receiving 8 or more sessions of therapy), and 3) Dropouts (participants dropping out of the treatment will be divided into early dropouts (before session 6) and late dropouts (after session 6)).

Therapist fidelity and adherence to the manual will be assessed for individually delivered CBTgrief and group-based CBTgrief. Thirty percent of all completed individual and group therapies (i.e., completed more than 8 sessions of therapy) will be randomly chosen to be rated for fidelity and adherence to the manual. The presence of the core components of the manual will be assessed as well as the quality of the application of these components session-by-session. Two master psychology students will receive comprehensive training in the manual by KK in doing these. KK will analyze 20% of the selected individual and group therapies for interrater agreement. These will be chosen randomly.

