### **The analysis population**

As recommended by the CONSORT guidelines for reporting noninferiority and equivalence randomized trials (Piaggio et al., 2012) we will do Intention-to-treat (ITT), but also per-protocol (PP) analyses as sensitivity analysis.

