### **Secondary analysis**

The secondary analyses will follow the same principle as the primary analysis for PTSD, depression, anxiety, functional impairment, quality of life, treatment satisfaction, and well-being – testing for non-inferiority of group vs. individual CBTgrief.

For loneliness and social support, we will test the superiority of the group-based CBTgrief with MLMs using a two-sided alpha = 0.5 for significant differences, following our hypotheses.

Reliable changes in symptoms of PGD, PTSD, anxiety, and depression were computed by the Reliable Change Index (RCI; Jacobson & Truax, 1991) on the completer sample for both group and individually delivered CBT format and from pre- to post-intervention and 6-month follow-up.

Additionally, we will calculate the percentages of A) recovered participants (scoring above cut-offs before but below after treatment), B) unchanged participants (no change in terms of cut-offs before and after treatment), and C) deteriorated participants (scoring below cut-offs before treatment but above after treatment).

Based on the two-step criterion, individuals will be classified as 1) recovered (met both Cutoff A and RCI), 2) improved (met RCI but not Cutoff A), 3) unchanged (met none of the criteria), or 4) deteriorated (met RCI but symptom scores increased). See the procedure used by e.g., (Papa et al., 2013); Reitsma et al. (2023); (Treml et al., 2021).

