### **Sensitivity analyses**

We will analyze both intention-to-treat (ITT) and per-protocol (PP) samples as it has been argued that this provides a more rigorous test of non-inferiority (Brasher & Dobson, 2014; D'Agostino Sr et al., 2003; Groenewold et al., 2022). For the per protocol analysis participants must have completed 8 or more sessions. Additionally, we do a stricter per-protocol analysis as sensitivity analyses (completed all 12 sessions).

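### Reliable change is planned only for completers (8 or more sessions on the SAP's only definition), with no all-randomised counterpart; the two-step classes also need tighter wording

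*SAP*

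**What the plan says.** Under Secondary analysis, the SAP computes reliable change in PGD, PTSD, anxiety and depression "on the completer sample for both group and individually delivered CBT format", from pre-intervention to post-intervention and to 6-month follow-up. No other population is named for this outcome.

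The word is defined once, under Adherence and protocol deviations: "2) Completers (participants receiving 8 or more sessions of therapy". The same list has a separate category for "1) Non-starters (participants that were randomized but received no therapy sessions", and categories for early and late dropouts. Sensitivity analyses uses the same number of sessions: "For the per protocol analysis participants must have completed 8 or more sessions".

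For the trial as a whole, The analysis population states that "we will do Intention-to-treat (ITT), but also per-protocol (PP) analyses as sensitivity analysis". Sensitivity analyses gives the reason for using both populations: "it has been argued that this provides a more rigorous test of non-inferiority".

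The two-step classification opens "Based on the two-step criterion, individuals will be classified as" and lists "1) recovered (met both Cutoff A and RCI), 2) improved (met RCI but not Cutoff A), 3) unchanged (met none of the criteria", followed by a fourth class, deteriorated, for those who met RCI with rising scores. Neither this scheme nor the separate cut-off percentages just before it names a population. The section then refers to three cited studies as examples of the procedure.

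**The concern.** Attendance is observed after randomisation and may depend on the format being tested. Rates restricted to those who attended at least 8 sessions are therefore not a comparison of the randomised groups. If completion differs by format and non-completers respond differently from completers, the two completer rates can agree while the rates among all randomised do not.

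The mixed models for the same four outcomes use maximum likelihood for missing data, so the intention-to-treat mean differences and the reliable-change rates will describe different sets of participants. Recovery and deterioration percentages are results that clinicians readily take from a report, and here they would come only from the population that the SAP elsewhere uses for sensitivity.

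A lesser matter is the two-step list. Taken word for word, it leaves some participants without a class and puts others in two, so the percentages need not sum to 100.

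**Working it through.** **Population.** There is no stated figure to reproduce, so the first step is to set the sections side by side.

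- Reliable change: completers only (Secondary analysis).
- Completer: 8 or more sessions (Adherence and protocol deviations).
- Per-protocol: 8 or more sessions (Sensitivity analyses).
- Main population: intention-to-treat, with per-protocol as sensitivity (The analysis population).

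Reliable change is thus planned at the per-protocol threshold alone. Non-starters and participants who stop before 8 sessions are outside it, whether or not they return questionnaires.

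**Illustration.** All inputs are assumed; the SAP gives no completion, response or return rates. Let c be the completion proportion, p the reliable-improvement rate in completers and r the rate in non-completers. The all-randomised rate is c·p + (1 − c)·r. If p and r are the same in both formats, completers show no difference, while the all-randomised gap (individual minus group) is

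(c_individual − c_group) × (p − r).

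With p = 0.50 and c_individual = 0.85:

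- c_group = 0.75, r = 0.10: 0.10 × 0.40 = 0.040
- c_group = 0.75, r = 0.20: 0.10 × 0.30 = 0.030
- c_group = 0.65, r = 0.10: 0.20 × 0.40 = 0.080
- c_group = 0.65, r = 0.20: 0.20 × 0.30 = 0.060

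The concealed gap is 3 to 8 points. If the two completion rates are swapped, it has the same size and the opposite sign. If completion is equal, or non-completers respond like completers, it is zero.

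**What observed scores recover.** Suppose 95% of completers and a proportion q of non-completers return the questionnaire. The rate among those with a score is

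(0.475c + (1 − c)·q·r) / (0.95c + (1 − c)·q), where 0.475 = 0.95 × 0.50.

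- Smallest gap: q = 0.3, r = 0.20, c = 0.85 and 0.75. Rates 0.484 and 0.471, gap 0.013 against a full gap of 0.030 (42%).
- Largest gap: q = 0.8, r = 0.10, c = 0.85 and 0.65. Rates 0.448 and 0.375, gap 0.073 against 0.080 (91%).

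Using every observed score reduces the selection but does not remove it.

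**Two-step classes.** Crossing the two criteria with the direction of change, and reading the list literally:

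- Cutoff A met, RCI met, score down: recovered.
- Cutoff A met, RCI met, score up: recovered and deteriorated.
- Cutoff A not met, RCI met, score down: improved.
- Cutoff A not met, RCI met, score up: improved and deteriorated.
- Cutoff A not met, RCI not met, either direction: unchanged.
- Cutoff A met, RCI not met, either direction: no class.

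Of the eight states, two have no class and two have two classes. A participant who starts just above the cut-off and falls slightly below it is recovered under the cut-off-only scheme and, if Cutoff A is that cut-off, has no class under the two-step scheme. The size of the unclassified cell depends too much on assumptions about score distributions and the cut-off for a figure to be useful.

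**The case against.** A completer analysis of a descriptive outcome is a legitimate choice and is openly stated. Reliable change appears in no hypothesis and not in the main results table. A reader might infer that the plan contradicts its own intention-to-treat commitment. The text does not support that: the pairing of intention-to-treat and per-protocol is justified by the non-inferiority test, and reliable change is not mentioned there.

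Attrition will be reported by format and a CONSORT flow is planned, so differential completion will be visible. The per-protocol mixed models will also give means at the same session threshold. Both points stand, but visible attrition does not correct the rates, and no all-randomised reliable-change result is planned.

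The completer sample might mean questionnaire completers. The Secondary analysis section has no cross-reference, the missing-data section uses *completed* of scales and questionnaires, and the fidelity paragraph uses more than 8 sessions where the definition has 8 or more. The session-based reading is the likelier because it is the only definition given. If the other was meant, one sentence would settle it.

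The illustration rests entirely on assumed inputs, and better completion in individual therapy is only one of the possible patterns. A reader might infer that the completer restriction favours the group format; nothing in the SAP supports a direction.

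On the classes, the list may be shorthand, with RCI taken as directional and *unchanged* as a residual. The cited procedures, not available here, may say so. That makes it a request for clearer wording, not a demonstrated error.

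**Conclusion.** The point holds as a minor one. On the SAP's only definition of completer, reliable-change rates by format will compare subsets selected after randomisation, with no all-randomised counterpart and no reason given. They can hide a difference in either direction if completion differs by format and non-completers respond differently from completers. Size and direction cannot be determined from the SAP; the 3 to 8 points show only what plausible-looking assumptions would produce.

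A reader might take this as a threat to the trial's main conclusion. It is not: these rates are secondary and descriptive, and the mixed-model non-inferiority tests do not use them. The gap and overlaps in the two-step classes are real on a literal reading and are a secondary wording point.

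**What to change.** In Secondary analysis:

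1. Report reliable change and the two-step classes by format for all randomised participants with an observed score at the time point, whatever the number of sessions attended.
2. Show the number with a missing score by format at each time point.
3. Keep completers (8 or more sessions) as a sensitivity analysis. If questionnaire completers were meant, say so.
4. Read RCI as directional: recovered and improved need a reliable decrease, deteriorated a reliable increase. Define *unchanged* as no reliable change, whether or not Cutoff A is met. Each participant then has exactly one class.

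I would not add a rule that counts missing scores as not improved. It does not bound the difference between formats, and it conflicts with the SAP's decision not to impute at survey level. It can also create a gap: on the inputs above with r = 0.50, so that the true gap is zero, the rate becomes 0.475c + (1 − c)·q·0.50. For q = 0.3 and c = 0.85 and 0.65 this gives 0.426 and 0.361, a false gap of 6.5 points.

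The cost is SAP wording and a few table rows, with no new data. The downside is that rates may look less favourable than among completers, and that observed-score analysis still leaves some selection.

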## Baseline characteristics

See the example below of what baseline characteristics will be reported.

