**Table 1.**

Participant characteristics at baseline.

Characteristic	Total sample (n=)	Individual CBT (n=)	Group CBT (n=)
Age, mean (SD)			
Gender, n (%)			
Female			
Male			
Education a , n (%)			
Primary education			
Secondary education			
Source of income b , n (%)			
Salary			
Pension			
Out of employment			
Other			
Relationship to the deceased, n (%)			
Spouse/partner			
Parent			
Other			
Years together, mean (SD) c			
Illness prior to death, n (%)			
Yes			
No			
Cause of death, n (%) d			
Cancer			
Cardiovascular disease			
Dementia			
Suicide			
Accident			
COVID-19			
Other age-related illness			
Time since loss (months), mean (SD)			
Additional bereavement losses, mean (SD)			
Previous use of psychosocial support prior to intervention, n (%) e			
Symptom profiles f			
PGD g only			
PGD and PTSD h			
PGD and depression			
PGD and anxiety			
PGD and $\geq$ two syndromes			
PGD and $\geq$ three syndromes			

Notes. a) Education will be categorized as primary education (primary school, high school, vocational training) and secondary education (college, university); b) Source of income will be categorized as 1) salary for those holding a job, 2) pension for those on early voluntary retirement and those receiving self-financed or government-assisted pension, and 3) out of employment (including unemployment benefits, social security payments due to sickness, or government-sponsored support); c) Only relevant for partner

loss; d) cause of death will be reported by the participant; e) Psychosocial support includes contacts with a psychiatrist, psychologist, counseling (e.g., patient organizations), and social support groups; f) Syndromes will be assessed based on self-report measures with cut-off values on clinically relevant symptom levels. Thus, no psychiatric diagnoses will be given; g) Prolonged grief disorder; h) Posttraumatic stress disorder.

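### Recovered, unchanged and deteriorated are each defined twice, and the cut-off-only definitions file any worsening above the cut-off as unchanged

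*SAP*

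**What the plan says.** The Secondary analysis section of the SAP describes individual change in three consecutive paragraphs.

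- **Reliable change.** The text reads "Reliable changes in symptoms of PGD, PTSD, anxiety, and depression were computed by the Reliable Change Index (RCI; Jacobson & Truax, 1991) on the completer sample". It applies to each format, over two intervals: pre-intervention to post-intervention, and pre-intervention to 6 months.
- **Cut-off scheme.** Percentages are planned for three classes. The first, for improvement, is "A) recovered participants (scoring above cut-offs before but below after treatment". The second, for those who stay on one side of the threshold, is "B) unchanged participants (no change in terms of cut-offs before and after treatment". The third, for worsening, is "C) deteriorated participants (scoring below cut-offs before treatment but above after treatment". No denominator is named.
- **Two-step scheme.** This combines the RCI with a threshold called Cutoff A. Participants are recovered if they meet both, improved if they meet the RCI only, and unchanged if they meet neither. The last class is "4) deteriorated (met RCI but symptom scores increased".

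Two other places bear on who starts above the PG-13 cut-off. The shell of Table 1 lists six baseline symptom profiles, and all six contain PGD. Its note f says: "Syndromes will be assessed based on self-report measures with cut-off values on clinically relevant symptom levels". That table is introduced with "See the example below of what baseline characteristics will be reported", so it is an example and not an entry rule. The Eligibility section refers to the registry record.

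The SAP gives no numerical PG-13 cut-off and does not define Cutoff A. It does not say whether the cut-off behind Table 1, the cut-offs in classes A to C, and Cutoff A are the same value.

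**The concern.** A class called deteriorated will be read as the share of participants who got worse. In the cut-off scheme it is the share who crossed a threshold upwards, which is possible only for those who started below it. In a trial of treatment for complicated grief, most or all participants may start above the PG-13 threshold. The class could then be nearly or wholly empty whatever happens to the scores, and participants whose grief worsens would be counted with those who did not change.

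On PCL-5, CESD-10 and GAD-7 some participants can start below the cut-off, since Table 1 has a PGD-only profile, so the class need not be empty. The scheme still hides worsening among those already above the cut-off. It also puts people who were never cases into the same unchanged class as people who remained cases. A difference between arms in these percentages would then partly reflect how many started on each side of the cut-off.

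The two-step scheme uses three of the same labels with other meanings, and the SAP does not say which scheme supplies the deterioration rate to be reported. At stake is a table in which deteriorated, 0% could be taken as reassurance about one delivery format when the rule could not have returned anything else.

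**Working it through.** The SAP states no figure on this point, so there is none to reproduce. The check has three parts.

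**1. The two schemes side by side.** In the two-step scheme every class except unchanged requires the RCI. The labels then fall as follows.

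| Participant | Cut-off scheme | Two-step scheme |
|---|---|---|
| Starts above, reliable increase | unchanged | deteriorated |
| Starts above, reliable decrease, does not meet Cutoff A, still above the cut-off | unchanged | improved |
| Starts above, ends just below, change not reliable | recovered | not recovered |
| Starts below, ends just above, change not reliable | deteriorated | unchanged |

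The first and last rows show that the word deteriorated conflicts in both directions. The third shows the same for recovered.

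**2. Enumeration.** Assumptions, none of them in the SAP: integer scores from 11 to 55 (45 values), a cut-off of 35, and above meaning 35 or more. That gives 21 values above and 24 below.

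If every baseline is above the cut-off:

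- Possible pairs of baseline and follow-up score: 21 × 45 = 945.
- Recovered: 21 × 24 = 504.
- Unchanged: 21 × 21 = 441.
- Deteriorated: 0.
- Worsening pairs: 21 × 20 / 2 = 210, all of them in unchanged.

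If any baseline is allowed:

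- Possible pairs: 45 × 45 = 2025.
- Recovered: 504. Deteriorated: 24 × 21 = 504.
- Unchanged: 441 + 24 × 24 = 1017.
- Worsening pairs: 45 × 44 / 2 = 990, of which 504 are deteriorated and 486 unchanged.

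The zero does not depend on the assumed scale or cut-off. It needs only that nobody starts below.

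**3. Illustration of size.** Assumptions, again not from the SAP: change with mean -5 and SD 8, rounded to whole points; reliable change of 8 points; baselines spread evenly over 15 points from the cut-off upwards, or over 8 points below it; 200,000 simulated participants per row.

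| Start below cut-off | Deteriorated, cut-off scheme | Reliable worsening | Reliable worsening filed as unchanged |
|---|---|---|---|
| 0% | 0.0% | 6.0% | 6.0% |
| 5% | 0.7% | 5.9% | 5.6% |
| 10% | 1.4% | 6.0% | 5.4% |
| 20% | 2.8% | 5.9% | 4.8% |
| 30% | 4.2% | 5.9% | 4.1% |

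The reliable-worsening column can be confirmed directly. A rounded change of 8 or more means a change of at least 7.5, so the probability is 1 - Φ((7.5 + 5) / 8) = 1 - Φ(1.5625), about 5.9%. It stays the same down the table, while the cut-off percentage rises from 0.0% to 4.2% with the baseline mix alone.

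**The case against.** The strongest reply is that the very next paragraph supplies what the cut-off scheme lacks. The two-step class for deterioration has no condition on baseline status, and the RCI is planned for PGD, PTSD, anxiety and depression, in both formats and at two time points. A participant who starts above the PG-13 cut-off and worsens reliably is labelled deteriorated there. The mixed models also compare mean change between the arms. This stands. A reader might infer that the trial will report no PG-13 deterioration whatever happens, or that harm could not be seen at all. The document does not support either reading.

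Three further objections also stand.

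- That all participants start above the PG-13 cut-off is an inference from an example table, because the entry threshold is not in this document. With some participants below, the cut-off class is not empty.
- A reader might infer that recovered is to be calculated over the whole sample. The SAP names no denominator, so the most that can be said is that it is unspecified.
- The percentages in the illustration come from assumed inputs and do not estimate what this trial will find.

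What the reply does not remove is the clash itself. Planning a sound definition beside an unsound one under the same name does not tell a reader which percentage to believe. The two-step scheme also has a possible limit of its own. The RCI is tied to the completer sample, which the section on adherence defines as 8 or more sessions. If the two-step scheme uses that sample, it does not cover worsening among dropouts.

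**Conclusion.** The point holds as a minor one. From the wording alone, the cut-off scheme cannot label anyone who starts above the cut-off as deteriorated and files their worsening as unchanged. Recovered, unchanged and deteriorated therefore carry conflicting meanings in consecutive paragraphs, and one person can be unchanged in one scheme and deteriorated in the other.

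The exact zero for PG-13 in both arms is conditional on every participant starting above the cut-off, which Table 1 suggests and the SAP does not state. For the other three scales the class is usable only for those who start below the cut-off, and the unchanged class mixes never-cases with persistent cases.

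The consequence is confined to descriptive secondary percentages. Reliable worsening remains visible through the two-step scheme, subject to the sample on which it is computed, and the primary non-inferiority test does not depend on any of this.

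**What to change.** Use the RCI-based increase (class 4 of the two-step scheme) as the only measure called deteriorated. Report it by arm for each of the four symptom scales at the time points already planned, post-intervention and 6 months.

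If cut-off crossings are kept, give them other names and their own denominators:

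- remission, as a percentage of those above the cut-off at baseline;
- new caseness, as a percentage of those below it at baseline;
- remained above and remained below, in place of the single unchanged class.

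Show the number at risk in each arm beside each percentage. Omit new caseness for PG-13 if nobody starts below the cut-off.

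The cost is a few sentences of the SAP and one re-laid table, with no new data. The small downside is that conditional percentages rest on smaller denominators.

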### **Sensitivity analyses**

We will analyze both intention-to-treat (ITT) and per-protocol (PP) samples as it has been argued that this provides a more rigorous test of non-inferiority (Brasher & Dobson, 2014; D'Agostino Sr et al., 2003; Groenewold et al., 2022). For the per protocol analysis participants must have completed 8 or more sessions. Additionally, we do a stricter per-protocol analysis as sensitivity analyses (completed all 12 sessions).

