#### Primary analysis

The primary analysis will examine whether group CBTgrief is non-inferior to individual CBTgrief.

The analyses for primary and secondary outcomes will consist of multilevel, mixed linear models (MLMs) including time (pre-intervention, post-intervention, 3-month follow-up, and 6-month follow-up), group (Group CBTgrief vs. Individual CBTgrief), and their interaction (Time x Group). Two-level MLMs will be used to test the Time x Group interaction effect taking into account that symptoms are measured at several time points (level 1) that are nested within individuals (level 2).

We will report between and within-group effect sizes (Cohen's  $d$ ) for both group and individual-delivered CBTgrief to assess change in symptoms over time in the respective treatment groups.

The rationale for the non-inferiority limit: The choice of the non-inferiority margin of 0.5 SD was based on a clinical judgment, considering that the minimal important difference has yet not been established on PG-13. 0.5 SD corresponds to the border between a mild and medium effect, which very often corresponds to the border for a clinically meaningful effect (Norman et al., 2003) – also for stressor-related disorders such as PTSD (0.5-0.8 SD; Stefanovics et al., 2018). Moreover, a recent meta-analysis found that grief-focused CBTs delivered individually had a medium pooled effect on PGD symptoms with the lower bound of the 95% confidence interval (CI) of 0.49 (Hedge's  $g$  = 0.67, 95% CI: 0.49-0.85; Komischke-Konnerup et al., 2024). Importantly, RCTs investigating individual-delivered grief-focused CBTs that specifically included similar interventions and theoretical backgrounds as CBTgrief have found large effects on PGD symptoms compared to active and passive control groups (Cohen's  $d$  = 0.90 – 1.34; Boelen et al., 2007; Reitsma et al.,

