### **Additional analyses**

We will analyze the potential influence of treatment preference before randomization to treatment format and analyze potential differences in treatment satisfaction post-intervention.

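### Both per-protocol sets are selected by attendance after randomisation and compared without covariates, so their agreement or disagreement with ITT can mislead, although the ITT verdict itself is not biased by this.

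*SAP*

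**What the plan says.** The section on sensitivity analyses defines two per-protocol sets. The first: "For the per protocol analysis participants must have completed 8 or more sessions". The second: "Additionally, we do a stricter per-protocol analysis as sensitivity analyses (completed all 12 sessions"). Both depend only on sessions attended.

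The same section gives the reason for analysing ITT and per-protocol samples together: "as it has been argued that this provides a more rigorous test of non-inferiority". The section on the analysis population sets the order: "we will do Intention-to-treat (ITT), but also per-protocol (PP) analyses as sensitivity analysis".

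Only one model is described, under Primary analysis: "The analyses for primary and secondary outcomes will consist of multilevel, mixed linear models (MLMs) including time", "group (Group CBTgrief vs. Individual CBTgrief), and their interaction (Time x Group"). It has two levels, time points within individuals. No covariate, weight or separate model is named for the per-protocol sets, and no rule says how ITT and per-protocol results are to be read together.

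On related points, attrition is to be reported by arm (Adherence and protocol deviations) and baseline group differences are to be explored with simple tests (Descriptive analyses). Under Additional analyses the SAP states: "We will analyze the potential influence of treatment preference before randomization to treatment format". None of these is tied to the per-protocol comparison.

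**The concern.** Session attendance happens after randomisation and may depend on the format. Joining a shared group and attending individual sessions are different hurdles, so one threshold can remove different kinds of people from each arm. The per-protocol arms are then self-selected, and a model with only time and group attributes any resulting difference in prognosis to the format. The missing-at-random statement in the SAP covers outcomes that were not returned. It does not cover randomised people whom the analyst leaves out.

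At stake is the value of the per-protocol result as a check. If the group arm loses more of its poor-prognosis participants, the per-protocol estimate shifts towards group CBTgrief and its agreement with ITT reassures falsely. If selection runs the other way, the per-protocol result may contradict a sound ITT result.

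**Working it through.** **Inputs from the SAP.** Margin 0.5 SD, one-sided alpha 0.025, allocation 1:1, session thresholds 8 and 12. Sample size is left to the registry record and no attendance rates are given, so there is no figure of the plan's own to reproduce.

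**Assumptions.** 40 to 60 randomised per arm. One baseline factor X (standard normal, higher meaning better prognosis) raises the log-odds of attendance by 0.5 to 1.0 per SD and improves 6-month PG-13 by b = 0.3 to 0.5 SD per SD. Retention, individual/group: 85-90%/65-75% for 8 sessions and 70%/35% for 12 sessions. The calculation compares the arms at a single time point.

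**Formulas.** Positive bias favours group.
- Bias = b × (mean X of group attenders − mean X of individual attenders)
- SE = √(1/n_ind + 1/n_grp), with n the numbers retained
- Error at a true d of −0.5 = 1 − Φ(1.96 − bias/SE)

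**Equal attendance slopes in both arms.**

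| Set | Retained ind/grp | Slope, b, n per arm | Mean X ind, grp | Bias | SE | Error |
|---|---|---|---|---|---|---|
| 8, low | 85/75% | 0.5, 0.3, 40 | 0.073, 0.120 | 0.014 | 0.250 | 2.8% |
| 8, high | 90/65% | 1.0, 0.5, 60 | 0.091, 0.292 | 0.101 | 0.210 | 6.9% |
| 12, low | 70/35% | 0.5, 0.3, 40 | 0.143, 0.308 | 0.050 | 0.327 | 3.5% |
| 12, high | 70/35% | 1.0, 0.5, 60 | 0.253, 0.543 | 0.145 | 0.267 | 7.8% |

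For the second row: bias = 0.5 × (0.292 − 0.091) = 0.101; SE = √(1/54 + 1/39) = 0.210; error = 1 − Φ(1.96 − 0.480) = 6.9%.

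**Unequal slopes** (b = 0.5, 60 per arm).
- Group 1.0, individual 0.5: at 90/65%, bias 0.5 × (0.292 − 0.049) = 0.122 and error 8.4%; at 70/35%, 0.5 × (0.543 − 0.143) = 0.200 and 11.3%.
- Group 0.5, individual 1.0: at 85/75%, −0.007 and 2.3%; at 70/35%, 0.028 and 3.2%.

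**Zero and reversal.** Identical selection gives zero bias. Swapping the arms in the two equal-slope high rows gives −0.101 and 0.7%, and −0.145 and 0.6%.

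**Does adjustment help?** This was checked by simulation with 63 per arm, which is 2 × ((1.96 + 0.84)/0.5)² rounded up, i.e. 80% power at a true difference of 0. The true d was −0.5 and retention (group/individual) was 70/85%, 60/85% and 40/70%.
- Attendance driven by a measured baseline factor (correlation 0.6 with attendance, 0.5 with outcome): unadjusted error 5.4%, 8.0% and 9.2%; adjusted for that factor 2.7%, 2.7% and 2.8%.
- Attendance driven by the outcome itself (correlation 0.4): 6.8%, 11.1% and 12.8% fall only to 5.8%, 9.4% and 10.5%.

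**Precision of the 12-session set.** At 60 per arm and 70/35% retained, 1.96 × 0.267 = 0.52, which exceeds the margin. Even an observed d of 0 would not pass there.

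**The case against.** The strongest reply is that per-protocol does not decide the trial. A reader might infer from the sensitivity section that the SAP calls per-protocol the more rigorous test. It does not: the phrase refers to analysing both samples, and the section on the analysis population makes per-protocol a sensitivity analysis. That stands.

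A reader might also infer that a worse group format could pass the −0.5 limit because of this. Nothing in the SAP lets per-protocol override ITT. If ITT decides, its error is untouched. If both had to pass, the joint error could not exceed that of ITT; simulations of differential attendance put it at 1.4% to 2.1%. That also stands, so the error rates above describe the per-protocol test alone.

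Three further points have weight.
- Every magnitude is assumed, and the largest values need a steeper attendance slope in the group arm.
- Baseline is a time level in the model, so a contrast of change over time may cancel factors that shift baseline and follow-up equally.
- Attendance-based per-protocol sets beside ITT are common, both sets here are defined in advance, and attrition is reported by arm.

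These limit the size of the point without removing it. Reporting attrition shows that the arms were depleted differently but does not correct the comparison. The preference analysis is not linked to the per-protocol models.

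**Conclusion.** The point holds as a weakness of a supporting analysis. Both per-protocol sets are selected after randomisation and, since no other model is given, would be compared with the covariate-free Time x Group model. That this model applies to them is an inference, because the SAP does not say so explicitly.

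Under the stated assumptions with equal slopes and lower group retention, bias is about 0.01 to 0.10 SD (8 sessions) and 0.05 to 0.15 SD (12 sessions). It reaches about 0.12 and 0.20 SD only if prognosis drives attendance more strongly in the group arm. The bias needs attendance to differ by arm, in rate or in mechanism, and to relate to prognosis. Its direction cannot be known in advance. The consequence is false reassurance or false contradiction of ITT. The documents do not support the conclusion that the ITT verdict is biased by this or that its error rate is raised.

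**What to change.** Keep both per-protocol sets and their unadjusted results. Then:

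1. Add to the per-protocol models a short prespecified list of baseline covariates already collected: treatment preference, baseline CESD-10 and PCL-5, age, and time since loss. For the 8-session set, inverse-probability-of-attendance weights estimated within arm are an alternative.
2. Tabulate baseline characteristics of each per-protocol set by arm.
3. State that the adjusted per-protocol result is read as supportive of ITT.

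The cost is a few sentences in the SAP and a few model terms on data in hand. The downside is small: the result depends on the covariates chosen, selection on unmeasured factors or on the outcome itself is not corrected, and the adjusted estimate may be imprecise in a small 12-session set.
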